## 7 Study Design

### 7.1 Description of the Study Design

This is a Phase 2, double-blind, block (compound/vaccine unit)-randomized, comparator-controlled study designed to evaluate the safety, reactogenicity, immunogenicity, transmission-blocking activity, and subsequent vaccine efficacy of Pfs230D1M conjugate formulated on AS01. Subjects will be drawn from approximately 137 compounds/vaccine units (extended families/neighboring compounds) in Doneguebougou and surrounding villages that have agreed as a family/compound to participate in the study. Individuals within the compound will not be randomized to individual arm assignments, but rather an entire family/compound will be randomized as a whole to receive either Pfs230D1M-EPA/AS01 or comparator vaccine in eligible and willing residents in that family/compound (vaccine unit) as well as the enrolled young children (1-4 years of age) in the parasitemia cohort (Group 4).

As previously noted, all eligible and enrolled pilot and main phase subjects  $\geq 5$  years of age or older will receive AL treatment prior to first vaccination as well as either Pfs230D1M-EPA/AS01 or comparator vaccine at 0, 28, 56, and 392 days (main phase) and 0, 28, 126, and 448 days (pilot phase). All vaccinated subjects will be followed for safety and tolerability, as well as immunogenicity via ELISA and functional antibody responses via SMFA.

Subjects 5-8 years of age will also receive AL treatment  $\sim 14$  days prior to vaccination #3 and  $\sim 7$  days prior to vaccination #4 in their compound, regardless of other antimalarial treatments

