## **11.2 Assignment to Groups**

### **11.2.1 Pilot Safety Study**

The subjects in Pilot Safety Study will be assigned randomization per their family compound randomization. In order for a compound to qualify for randomization, approximately 80% of the residents within a family compound/vaccine unit who are preliminarily eligible for vaccination must have signed consent and be preliminarily eligible for enrollment (e.g. screening available vaccinee unit for major medical problems, pregnancy, and time availability). When the first child (<19 years of age) from the family compound is scheduled for vaccination, the family compound as a whole will then be randomized to Pfs230D1M-EPA/AS01 or comparator.

The Pilot Study cohorts will be enrolled in the following order:

1. Arms 1a (n=15) and 1b (n=15); then
2. Arms 2a (n=15) and 2b (n=15)

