## **17 Statistical Considerations**

### **17.1 Pilot Study**

#### **17.1.1 Primary Objective**

The primary objective of the pilot study is to assess the safety and reactogenicity of Pfs230D1M-EPA/AS01 in Malian children (Arms 1a, 2a) compared to comparator vaccine (Arms 1b, 2b).

- The frequency of systemic and local AEs will be summarized.
- A line listing of each clinical and laboratory AE classified as local, solicited, or other will be displayed in tables stratified by vaccine allocation.
- AEs will be summarized by severity and relationship to vaccine.
- The proportion of subjects with at least 1 AE will be compared by study group, and tests will be performed to assess whether these groups differ with respect to these proportions. To evaluate the difference in AEs between the initial vaccination and the subsequent vaccinations, a Wilcoxon signed rank test (WSRT) will be performed, where the response for each subject is the difference between the numbers of AEs in the 7 days following each vaccination. To compare number and severity of AEs between control and vaccine arms, the Wilcoxon-Mann-Whitney test (WMW, also known as Wilcoxon rank sum test and Mann-Whitney U test) as well as linear regression may be used.
- SAEs occurring within the study period will be listed by relationship to vaccine.

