### 17.2.2 Secondary Objectives

To assess vaccine efficacy of Pfs230D1M-EPA/AS01 against *P. falciparum* infection measured by BS (All Arms except Arms 3e/3f)

The vaccine efficacy will be assessed by comparing the rates of positive BS in children 5-18 years of age receiving Pfs230D1M-EPA/AS01 vs those receiving the comparator vaccines. An additional measure of vaccine protection will be assessed in the participants 1-4 years of age in Arms 4a/4b by comparing the rates of positive BS in the compounds receiving Pfs230D1M-EPA/AS01 vs those receiving the comparator vaccines.

To assess safety and reactogenicity of administration of Pfs230D1M-EPA/AS01 (All Arms)

- The frequency of systemic and local AEs will be summarized.
- A line listing of each clinical and laboratory AE classified as local, solicited, or other will be displayed in tables stratified by vaccine allocation.
- AEs will be summarized by severity and relationship to vaccine.
- The proportion of subjects with at least 1 AE will be compared by study group, and tests will be performed to assess whether these groups differ with respect to these proportions. To evaluate the difference in AEs between the initial vaccination and the subsequent vaccinations, a WSRT will be performed, where the response for each subject is the difference between the numbers of AEs in the 7 days following each vaccination. To compare number and severity of AEs between control and vaccine arms, the Wilcoxon-Mann-Whitney test (WMW, also known as Wilcoxon rank sum test and Mann-Whitney U test) as well as linear regression may be used.
- SAEs occurring within the study period will be listed by relationship to vaccine.

ELISA and SMFA assays will be conducted on a subset of samples deemed to be of scientific interest by DSF or BS assays due to the intensive laboratory analysis required to generate the data. Analysis of these data will take into account the compound randomization.

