### 17.2.3 Exploratory Objectives

To explore cellular and humoral responses to Pfs230D1M (All Arms except Arms 4a/4b)

To identify host and parasite factors associated with transmission (All Arms)

To track transmission of parasites from human to human using highly variant gene fragments (All Arms)

GEE analyses with compound level clustering will be used to analyze ELISA, SMFA and safety endpoints.

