## 17.3 Sample Size and Power Calculations

### 17.3.1 Pilot Study

#### 17.3.1.1 Safety

The arms are sufficiently sized for safety. For each dose level ( $n=15$ ) in Arms 1a, 2a, vaccination of 15 subjects gives a probability of at least 0.90 for detecting 1 or more serious or severe AEs that occur with a probability of 0.142 or more per subject.

If we combine all treated groups (arms 1a and 2a), 30 subjects, we have 95% power to detect 1 or more serious or severe AEs that occur with a probability of 0.095 or more per subject. Due to arms having different age ranges, this analysis would only be done to catch an AE that transcended these discrepancies.

We will compare all AE event proportions between the control arm and treated arm by Fisher's exact test.

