### 17.4 Randomization

See [Section 11.2](#) for more information on individual study schedule.

This study will be cluster-randomized with family compounds, or groups of compounds (vaccine units) serving as the unit of comparison. A listing of the compounds in the study area with the numbers of individuals residing in their compounds will be created and used for randomization. The number of vaccine units will be the similar for each group. Enumerated compounds should have a target of approximately 80% participation rate of eligible participants for inclusion as a study unit, but consideration will be given to the number of children to finalize the decision for inclusion. Randomization for the full trial needs to be completed prior to the age de-escalation so that the randomization for vaccinated participants in the pilot phase study holds through the main phase.

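### Whole vaccine units are randomised, but pilot safety names only tests for independent subjects, and the main-study safety wording is not reconciled with the clustered GEE

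*Combined protocol and SAP*

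**What the plan says.** Section 7.1 states that "an entire family/compound will be randomized as a whole to receive either Pfs230D1M-EPA/AS01 or comparator vaccine". Section 17.4 repeats it: "This study will be cluster-randomized with family compounds, or groups of compounds (vaccine units) serving as the unit of comparison". The pilot is no exception. Section 11.2.1 says: "The subjects in Pilot Safety Study will be assigned randomization per their family compound randomization".

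Safety is one of two pilot primary endpoints (8.1.1); the other is direct skin feeding (DSF). For pilot safety, 17.1.1 says "The proportion of subjects with at least 1 AE will be compared by study group" without naming the test, and offers WMW and linear regression for the number and severity of AEs. Section 17.3.1.1 supplies the test for proportions: "We will compare all AE event proportions between the control arm and treated arm by Fisher's exact test". Nothing in 17.1 or 17.3.1 adjusts the safety comparison for unit. The mixed model in 17.1.3 concerns immune responses.

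For the main study, where safety is secondary, 17.2.2 repeats the pilot bullets: "To compare number and severity of AEs between control and vaccine arms, the Wilcoxon-Mann-Whitney test" is offered, "as well as linear regression may be used". Two other places point the other way. Under Exploratory Objectives, 17.2.3 says "GEE analyses with compound level clustering will be used to analyze ELISA, SMFA and safety endpoints". Section 17.3.2.3 asks that the primary safety analyses respect compound-based randomisation, but names no method and leaves its application to judgement.

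**The concern.** Members of one vaccine unit always share an arm. They also tend to share exposure, dosing dates, visit days and reporting habits. If AEs correlate within units for such reasons, a test that counts each person as independent uses too small a standard error and finds too many differences between arms, in either direction.

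The pilot safety section offers nothing else. In the main study an analyst could follow 17.2.2 or 17.2.3 and obtain different p-values from the same data. The omission in 17.2.2 is noticeable because the same section says that the ELISA and SMFA analysis will account for compound randomisation, and says nothing of the kind about AEs.

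**Working it through.** **1. The plan's own safety figures.** Section 17.3.1.1 gives the chance of seeing at least one serious or severe AE, 1 − (1 − p)^n.
- n = 15, p = 0.142: 0.8995, against 0.90 stated.
- n = 30, p = 0.095: 0.9499, against 0.95 stated.

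Both reproduce, and both assume independent children. With 5 children per unit and an assumed ICC of 0.01 to 0.10 (beta-binomial), they fall to 0.85–0.89 and 0.92–0.95. The plan states no power or error rate for the AE comparisons between arms.

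**2. Inputs for the arm comparison.**
- About 137 units (8.3).
- 1101 vaccinees (3.3), so m = 1101/137 = 8.04 per unit. The planned 1500 would give 10.95.
- ICC 0.01, estimated for parasitemia (17.3.2.1). None is given for AEs, so 0.05, 0.10 and, for the pilot, 0.20 are assumptions.
- Compounds range from 5–10 people to more than 100 (9.1). The coefficient of variation (CV) of unit size is not stated and is taken as 0 to 1.0.
- Two-sided 0.05, stated for ELISA (17.3.1.2) and assumed for AEs.

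**3. Main study.** Design effect DE = 1 + ((1 + CV²)m − 1) × ICC. True size of a nominal 5% unclustered test = 2 × (1 − Φ(1.96/√DE)). For m = 8.04:

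| ICC | DE, equal units | True size, equal units | True size, CV 1.0 |
|---|---|---|---|
| 0.01 | 1.07 | 5.8% | 6.8% |
| 0.05 | 1.35 | 9.2% | 13.9% |
| 0.10 | 1.70 | 13.3% | 21.6% |

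Simulating WMW on clustered AE counts with 137 unequal units averaging 8 gave 4.9% at ICC 0, then 6.3%, 10.6% and 16.7% at the three ICCs above. The formula and the simulation agree in scale.

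**4. Pilot.** The number of pilot children per unit is not stated. WMW was simulated, and the size of Fisher's test was computed exactly with beta-binomial units and AE risks of 0.3 to 0.8.
- WMW, one child per unit: about 4–5%, so no inflation.
- WMW, 2 to 5 per unit, ICC 0.01 to 0.20: about 4% to 14%. The top of the range needs 5 per unit and ICC 0.20.
- Fisher, 15 v 15: about 1.7% with one child per unit; at most 4.5% with 3 per unit at any ICC up to 0.20, or with 5 per unit at ICC up to 0.10; 7–8% with 5 per unit and ICC 0.20.
- Fisher, 30 v 30: at most 4.4% with 3 per unit and ICC up to 0.10. With 5 per unit it is 5.3–6.3% at ICC 0.10 and 8.9–10.3% at 0.20; with 3 per unit and ICC 0.20 it is 5.3–6.3%.

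Fisher's test is conservative at these sample sizes, and that absorbs most of the clustering.

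**The case against.** For the main study, the firm commitments already respect the design. Section 17.2.3 says clustered GEE will be used for safety, and 17.3.2.3 asks for methods that respect compound randomisation, whereas WMW and linear regression are only permitted. The unnamed test of AE proportions in 17.2.2 could be a binary GEE, and linear regression can be fitted with clustering. Only WMW on individuals conflicts directly. This stands: a reader might infer that the main-study AE p-values will be too small, and the documents do not show that.

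The size also rests on an unstated AE ICC. At the only ICC in the plan, 0.01, the effect is small. This stands too, although that estimate is for parasitemia. The argument in 17.3.2.1 that clustering is negligible also relies on a median of 4 subjects aged 9–18 per compound, whereas the safety comparison covers all vaccinees, about 8 per unit.

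Finally, little hangs on these p-values. Pilot progression rests on DSMB review (7.2.1), and the pausing and halting rules (15.9, 15.10) use counts and percentages. That limits the consequence. It does not justify leaving a primary-endpoint comparison without a method that fits the randomisation.

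**Conclusion.** The point holds in a limited form. In the pilot, the safety comparison between arms has no cluster-respecting method. In the main study, 17.2.2 carries over pilot wording that is not reconciled with 17.2.3 and 17.3.2.3.

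Inflation is conditional on two things: the individual-level tests being used, and AEs correlating within units. With 137 equal units of about 8, the true size of a nominal 5% WMW test is about 6% at ICC 0.01, and about 9% and 13% at the assumed 0.05 and 0.10; unequal units raise it. In the pilot, WMW is the main exposure. Fisher's test exceeds 5% chiefly at about 5 children per unit with ICC 0.10 to 0.20.

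Two other readings go too far. The pilot does not lack a clustered method for all its primary endpoints: DSF is analysed with the main group by a compound-clustered Poisson GEE (8.1.1, 17.2.1). And no error rate or power loss for Fisher's test should be charged to the main study, because the plan names that test only for the pilot.

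**What to change.** 1. In 17.2.2, state that GEE clustered on the vaccine unit governs AE comparisons between arms, moving the sentence up from 17.2.3. Delete WMW and linear regression there, or label them descriptive without p-values.
2. In 17.1.1 and 17.3.1.1, keep the same statistics (difference in proportions with an AE, rank sum of AE number or severity), but take p-values from re-randomising whole vaccine units in the way they were allocated. Report how many units contributed pilot children.

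The cost is protocol wording and a short program; no new data are needed. Intervals will be wider and apparent power for AE differences lower. If pilot units are few, the re-randomisation p-value is also coarse. With 3 units per arm there are C(6,3) = 20 allocations, so the smallest two-sided p-value is 2/20 = 0.10. In that case the comparison is best reported as an estimate with its unit count.

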## 6.2.2 Secondary Objectives

- To assess vaccine efficacy of Pfs230D1M-EPA/AS01 against *P. falciparum* infection measured by blood smear (All Arms except Arms 3e/3f)
- To assess safety and reactogenicity of administration of Pfs230D1M-EPA/AS01 (All Arms except 4a/4b)
- To assess immunogenicity as measured by enzyme-linked immunosorbent assay (ELISA) titer response to Pfs230D1M (All Arms except Arms 4a/4b)
- To assess functional antibody response by standard membrane feeding assay (SMFA) to Pfs230D1M (All Arms except Arms 4a/4b)

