## 12.6 Immunologic Laboratory Testing

### 12.6.1 ELISA

Anti-Pfs230 ELISAs will be performed on sera obtained from immunized subjects at MRTC in Bamako, Mali and may also be performed at collaborating laboratories.

For Pfs230D1M ELISAs, microwell plates are first coated with antigen solution. Plates are washed with TRIS-buffered saline (TBS) containing Tween-20 (T-TBS) and blocked with TBS containing skim milk powder. After washing with T-TBS, diluted serum samples are added in triplicate and incubated at room temperature for 2 hours. After incubation, unbound antibodies are removed by washing the plates with T-TBS, and alkaline phosphatase-conjugated goat anti-human IgG solution is added to each well and incubated for 2 hours at room temperature. Plates are then washed with T-TBS, followed by adding phosphatase substrate solution to each well; the plates are then covered and incubated for 20 minutes at room temperature for color development. The plates are read immediately at 405 nm with a microplate reader. The optical density values are used to determine antibody levels by comparing to a standard curve generated from a known positive-control plasma included on each ELISA plate.

Additionally, the magnitude and kinetics of IgG responses may be explored over time post-vaccination. Quality of antibody responses may be explored via antibody avidity as well as assessment of antibody subclasses to provide useful insight into the humoral immune response.

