### 17.3.2.3 Analysis

The primary DSF analysis will use a GEE model with compound level clustering and the number of positive DSFs as outcome will be used for analysis with an offset for the number DSF tests. The primary parasitemia analysis will be analogous. The primary analysis population will follow the intention-to-treat principle. Additional analyses will explore the effects of different covariates such as time since start of the rainy season, SMC treatment, compound-level vaccine coverage, or proximity to a control compound on vaccine efficacy.

The primary safety and immunogenicity analyses will compare the rates of AEs or levels of antibody/activity between vaccinated and control individuals using standard statistical methods that respect compound-based randomization, as appropriate.

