Laboratory Procedures																															
CBC with differential	EDTA		2.0	2.0	2.0	2.0	2.0	2.0	2.0	2.0	2.0	2.0	2.0	2.0	2.0	2.0	2.0	2.0	2.0	2.0	2.0	2.0	2.0	2.0	2.0	2.0	2.0	2.0	2.0	2.0	
ALT/ Creatinine	SST		3.0	3.0	3.0	3.0	3.0	3.0	3.0	3.0	3.0	3.0	3.0	3.0	3.0	3.0	3.0	3.0	3.0	3.0	3.0	3.0	3.0	3.0	3.0	3.0	3.0	3.0	3.0	3.0	
HIV testing	SST		5.0																												
Urine dipstick or Urinalysis	Urine Container		X																												
Hemoglobin Typing	EDTA		X																												
Urine/Serum pregnancy test (females only)	Urine Container or SST		X	X	X				X					X					X		X		X		X						
Schistosomiasis +/- Helminth Testing	Urine +/- Stool Sample		X																												
Malaria Blood Smear	CAP/EDTA		0.5	0.5				0.5	0.5				0.5	0.5				0.5	0.5	0.5	0.5	0.5	0.5	0.5	0.5	0.5	0.5	0.5	0.5	0.5	
Malaria PCR/Genotyping/ Gametocyte	CAP/EDTA		1.0	1.0				1.0	1.0				1.0	1.0				1	1	1	1	1	1	1	1	1	1	1	1	1	
Pf230 ELISA	SST			10				5	5				5	5				5													
SMFA (2)																				X	X	X	X	X	X	X	X				
DSF (3)	X																			X	X	X	X	X	X	X	X				
Transcriptional analysis	PAXGene		1			1						1																		1	
Daily blood draw volume in mL			10.0	7.5	17.5	0.0	6.0	0.0	11.5	11.5	0.0	6.0	0.0	11.5	11.5	0.0	6.0	5.0	17.5	1.5	1.5	6.5	1.5	1.5	1.5	1.5	6.5	1.5	1.5	1.5	6.5
Cumulative blood volume in mL			10.0	17.5	35.0	35.0	41.0	41.0	52.5	64.0	64.0	70.0	70.0	81.5	93.0	93.0	99.0	104.0	121.5	123.0	124.5	131.0	132.5	134.0	135.5	142.0	143.5	145.0	146.5	154.0	160.5
1 Visit windows are based off timing of days post the preceding vaccination																															
2 SMFA may be completed on subjects at Study Day 0 and 182; other SMFA time points indicated above will be completed depending on associated ELISA and DSF results at that time point.																															
3 DSF will be completed twice monthly post Vaccination #3 through day 112 post Vaccination #3 (total = 8 feeds).																															

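### Choosing main-study ELISA and SMFA samples by DSF, smear or ELISA results exposes the arm comparison of these secondary endpoints to selection bias

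*Combined protocol and SAP*

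**What the plan says.** **Selection.** For the main study, Section 17.2.2 states that "ELISA and SMFA assays will be conducted on a subset of samples deemed to be of scientific interest by DSF or BS assays", and gives laboratory workload as the reason. It gives no selection rule, subset size, sampling fraction by arm or weights. Its only analysis provision is that "Analysis of these data will take into account the compound randomization". For SMFA, the Year 1 footnotes in Appendix A name Study Days 0 and 182 as days on which the assay may be done. For 9-18 year olds and adults they add that "other SMFA time points indicated above will be completed depending on associated ELISA and DSF results at that time point". For 5-8 year olds the same footnote refers to ELISA results only.

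**Use.** Sections 6.2.2 and 8.2.2 make ELISA titre and SMFA activity secondary objectives and endpoints for every arm except 4a/4b. Section 17.3.2.3 says that "The primary safety and immunogenicity analyses will compare the rates of AEs or levels of antibody/activity between vaccinated and control individuals". Section 17.2.3 says that "GEE analyses with compound level clustering will be used to analyze ELISA, SMFA and safety endpoints".

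**Text that points the other way.** Section 12.6.1 says that "Anti-Pfs230 ELISAs will be performed on sera obtained from immunized subjects at MRTC in Bamako, Mali", with no subset. The Précis limits SMFA, but not ELISA, to selected samples. Appendix A schedules ELISA by visit in every vaccinated arm. In the pilot, Section 17.1.2 plans ELISA at scheduled times, and Section 3.3.2 reports it completed for both pilot age groups.

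**The concern.** DSF positivity is the primary endpoint and smear positivity a secondary one. The vaccine is intended to change both. Choosing sera by either result conditions the immunogenicity comparison on a consequence of treatment, so the assayed samples need not represent the randomised arms. A model for compound clustering corrects the variance; it does not correct selection.

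The protocol gives reasons to expect the selection to be informative. Section 1.2.3.1.1.2 says that titre correlates well with the serum activity that blocks transmission, so DSF-positive vaccinees should tend to have low titres. Section 1.1 says that natural infection may boost the response, so smear-positive sera could be shifted differently. Choosing SMFA sera by their ELISA result is more direct still, because titre and SMFA activity are closely linked. Section 17.2.2 also selects samples rather than people, so time since vaccination among assayed sera could differ between arms.

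At stake are the size of the vaccine-control difference in titre and SMFA activity, the age-group estimates, and any correlate of titre with transmission.

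**Working it through.** **1. The plan's own figures.** Sections 17.3.1.2 and 17.3.1.3 give pilot power with 15 per group. Simulating the two-sided 0.05 Wilcoxon-Mann-Whitney test on normal draws with the stated means and SDs gives:

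| Pilot comparison | Plan | Reproduced |
|---|---|---|
| ELISA, baseline vs 3 months after dose 2 | over 0.99 | 0.9999 |
| ELISA, 2.3-fold | over 0.80 | 0.82 |
| SMFA, TRA difference 32 | at least 0.60 | 0.60-0.61 |
| SMFA, TRA difference 40 | 0.80 | 0.79-0.80 |

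The fold rise is exp(5.356736 - 3.688401) = exp(1.668335) = 5.30, against 5.31 stated. No power or sample size is given for ELISA or SMFA in the main study or for the selected subset.

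**2. Inputs for an illustration of selection.** From Section 17.3.1.2, log titre in vaccinees has mean m1 = 5.3567 and SD s1 = 0.8869. Baseline, used here as a stand-in for the comparator arm, has m0 = 3.6884 and s0 = 0.5490. Hence s1² - s0² = 0.7866 - 0.3014 = 0.4852. Vaccine activity (VA) of 0.4, 0.5 and 0.6 comes from Section 17.3.2.1.

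**3. Model (an assumption, not in the documents).** Only DSF-positive samples are assayed, log DSF risk falls linearly with log titre at slope b, and the whole vaccine effect runs through titre. For normal log titre:

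- b solves -b(m1 - m0) + b²(s1² - s0²)/2 = ln(1 - VA).
- Selection shifts each arm's mean log titre by -b × SD².
- The observed ratio is therefore 5.30 × exp[-b(s1² - s0²)].

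At VA 0.4, b = 0.321. Check: -0.321 × 1.6683 + 0.321² × 0.4852/2 = -0.511 = ln 0.6. The ratio is 5.30 × exp(-0.321 × 0.4852) = 5.30 × 0.856 = 4.54.

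| VA | b | Ratio seen | Change |
|---|---|---|---|
| 0 (selection unrelated to titre) | 0 | 5.30 | 0% |
| 0.2 | 0.136 | 4.96 | -6% |
| 0.4 | 0.321 | 4.54 | -14% |
| 0.5 | 0.444 | 4.28 | -19% |
| 0.6 | 0.602 | 3.96 | -25% |

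A weighted Monte Carlo run agreed.

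**4. Detection.** Section 17.3.2.1 reports 45 DSF-positive individuals in Year 1. With equal arms, 45/(2 - VA) are controls, giving control:vaccine splits of about 28:17 at VA 0.4 and 32:13 at VA 0.6. Simulated power for an arm difference on those numbers, with the shifted means, stays above 0.99.

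**5. Where the calculation does not reach.** DSF is done only in 9-18 year olds. In 5-8 year olds and adults, a DSF-or-smear rule can rest only on smears, and the documents do not fix the direction of that selection. For SMFA chosen on ELISA results, the rule is not stated, so no size can be computed.

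**6. The named SMFA days.** In Appendix B, Day 182 in the pilot is 56 days after dose 3, with serum drawn for ELISA and SMFA. In the main-phase child arms it is 126 days after dose 3, and blood is drawn only for smear and PCR. Adults have visits on Days 168 and 196, but none on Day 182.

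**The case against.** The strongest reply is that Section 17.2.2 is one loosely worded sentence and the rest of the protocol does not behave that way. ELISA is scheduled by visit in every vaccinated arm, Section 12.6.1 sets no subset, and the Précis reserves selection for SMFA. The pilot ELISA is unselected. The footnotes name two SMFA days. The phrase in Section 17.2.2 is undefined and could cover DSF-negative or matched samples from both arms. If choice were unrelated to titre within arm, there would be no bias. These are secondary endpoints, and the large rise in titre would be detected anyway. Outcome-dependent sampling is also legitimate for a correlate analysis when sampling probabilities are known.

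Much of this stands, and it limits both the wording and the severity. It does not remove the point. Section 17.2.2 is the statistical text for the main study and contradicts the other sections, so either could be followed. Nothing in the plan ensures that selection is unrelated to titre, and no sampling probabilities are specified. The pilot covers only 60 participants. The named Day 182 gives no scheduled serum draw in the main-phase child arms and does not exist for adults.

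**Conclusion.** The concern holds as a risk created by an undefined, outcome-linked sampling rule that conflicts with other sections. It should be fixed. It does not touch the primary endpoint, blood-smear efficacy or safety.

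Under DSF-positive-only selection in 9-18 year olds, a 5.3-fold difference would read as about 4.5- to 4.0-fold at VA 0.4-0.6, an understatement of 14-25%. This rests on the log-linear risk model, on the vaccine acting wholly through titre, on baseline standing in for the comparator arm, and on titres from the earlier adult trial three months after dose 2. With smear-based selection the direction is unknown. Power to show immunogenicity is not in question.

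Three stronger readings are tempting:

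- A reader might infer that all ELISA is run only on outcome-selected samples. The pilot plan, Section 12.6.1 and Appendix A contradict that.
- A reader might infer that the comparison is necessarily biased. The rule is not defined, so exposure to bias is as far as the documents go.
- A reader might shift only the vaccine arm. Assuming a 25% or 50% fall in DSF risk per SD of log titre, this gives 4.1- or 2.9-fold. The plan makes no arm distinction in selection, and shifting both arms under the same assumptions gives about 4.5- or 3.6-fold. The 50% case would also imply VA of about 0.69, above the plan's highest scenario.

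**What to change.** - Reconcile Section 17.2.2 with the Précis, Section 12.6.1 and the Appendix A schedule, and state which samples will be assayed.
- Base arm comparisons of ELISA and SMFA on all participants, or on a random subcohort stratified by arm and age group. Draw it without reference to DSF, smear or ELISA results.
- Assay at fixed visits after doses 3 and 4 that exist, with serum drawn, in each arm's schedule. In Appendix B, the visits 14, 56 and 112 days after each of these doses meet that condition in every vaccinated arm. Correct the SMFA footnotes to match.
- Use samples chosen by DSF, smear or ELISA result only as a supplement, with known sampling probabilities and inverse-probability weights in the GEE, or label the analysis exploratory.

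The cost is revised wording and a random draw. The subcohort can be sized to the existing assay budget; the plan gives no assay number, so that size must be stated. The downside is fewer outcome-chosen samples for exploratory work.
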